Study Arm 1: One, two and three-level posterior spine fusion surgery using bilateral pedicle screw instrumentation under 3D MvIGS intraoperative navigation guidance.

Study Arm 2: One, two and three-level posterior spine fusion surgery using bilateral pedicle screw instrumentation under 2D fluoroscopy.

Primary Endpoint: The primary endpoint is based on the mean reduction in total length of operative time. Operative time will be determined by the official recorded operative notes.

Secondary Endpoints: Secondary endpoints include:

- Length of stay
 - Aim: Decrease length of hospital stay
 - Measured: Time (Hours)
- Length of time for initial image processing
 - Aim: Decrease disturbance to surgeon workflow
 - Measured: Time (Minutes)
- Length of time to place all screws
 - Aim: Reduce the time for screw placement
 - Measured: Time (Minutes)
- Length of time to confirm screw placement
 - Aim: Reduce the time needed for confirmation of screw location
 - Measured: Time (Minutes)
- Length of time to register images
 - Aim: To reduce time for registration of reference images
 - Measured: Time (Seconds)
- Estimated Blood Loss (EBL)

- Aim: To reduce the EBL of each case
 - Measured: Milliliters (mL)
- Incidence of Malalignment
 - Aim: To decrease the incidence of pedicle screw malalignment
 - Measured: Misalignment angle between pilot hole and screw trajectory (degrees)
- Complications: Neurological Deficits, Dural Tears, deep wound infections, etc.
 - Aim: To decrease the incidence of intraoperative complications
 - Measured: number of reported complications while hospitalized
- Measurement of 2D fluoroscopy radiation exposure
 - Aim: to reduce patient and surgeon exposure to radiation
 - Measured: Exposure measured by Dose Area Product (DAP)

Exploratory Analyses: Exploratory analyses include the number of vertebral levels involved, radiographic evaluations of anterior disc height, implant migration, and stability, and preservation of motion at the adjacent, un-instrumented level.

Number of Patients Planned: A total of 130 patients, with 65 patients per group.

Criteria for Inclusion: Patients are included in the study if all of the following criteria are met:

- 1) Diagnosis of spinal stenosis of the lumbar spine with \leq grade 2 degenerative spondylolisthesis
- 2) Skeletally mature adults between the ages of 18-85 years at the time of surgery;
- 3) Has completed at least 6 months of conservative therapy;

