3 STUDY DESIGN

3.1 General Overview of the Study Design

This is a single center, non-randomized, prospective cohort study to comparatively evaluate the implementation of the MvIGS spine navigation system to conventional 2D fluoroscopy for pedicle screw fixation for the treatment of spinal stenosis with degenerative spondylolisthesis of the lumbar spine.

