4. STATISTICS

4.1 Sample Size Analysis

- **Student's t-test, ANOVA, chi-square, regression, etc.:** Independent samples T-test
- **Alpha level:** 0.05
- **Beta or power level:** 0.883
- **Primary outcome variable estimate (mean +/- s.d. for continuous outcome, frequency/ percentage for categorical variable):** Total length of operative time (minutes) as determined by the official recorded operative notes
- **Number of groups being compared (use 1 for paired analysis within the same subjects):** 2
- **Effect size or change expected between groups:** Estimated change difference in length of operative time of five (5) minutes with equivalence margins of 40 minutes
- **Resulting number per group:** 65 per group; 130 patients total

A priori power analysis is based on recorded estimates of operative time for 1, 2, and 3-level fusion surgeries. Average length of surgery for 1, 2, and 3-level fusion surgeries are 230, 275, and 325 minutes, respectively. Estimated pooled standard deviation was set at 70 minutes, representing 22 to 30% of the mean operation time for the single and multi-level surgeries. In a non-inferiority model using an independent sample t-test, group sample sizes of 65 patients in two study groups achieves 88% power (with statistical significance defined as alpha equal to 0.05) to detect non-inferiority where the margin of equivalence is 40 minutes and the true difference between study groups is estimated to be 5 minutes.

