4.2 Data Analysis

Data analysis of the study will include:

Descriptive statistics will report means and standard deviations for continuous variables of the study population. Frequencies and percentages will be used to report all discrete variables. Tests of normality for continuous variables will be evaluated using Shapiro-Wilks tests. For those that are non-parametric, Mann-Whitney U tests will be used.

Analysis of the primary outcome will use independent samples t-tests to compare the mean length of surgery between the two study arms.

Comparison of secondary outcomes between patients who undergo posterior spine fusion surgery using 2D fluoroscopy versus those who undergo the same procedure under 3D MvIGS intraoperative navigation guidance will use independent samples t-tests to analyze length of hospital stay; time for initial image processing; time to place all pedicle screws; time to confirm screw placement; time to register images; estimated blood loss; and amount of radiation exposure. Chi-square (or Fisher's exact) tests will be used to compare differences in incidence of malalignment and rate of complications between the two study groups.

To adjust for any potential confounding, multivariable regression models will be generated to report the adjusted effect of which spine navigation technique is used on length of surgical time.

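### The deciding test of operative time is an unadjusted t-test in a non-randomised cohort that mixes one-, two- and three-level fusions; number of levels should be in that model

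*Combined protocol and SAP*

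**What the plan says.** Section 4.2 (Data Analysis) gives the primary analysis as follows: "Analysis of the primary outcome will use independent samples t-tests to compare the mean length of surgery between the two study arms". For continuous variables that fail a Shapiro-Wilk test it adds: "For those that are non-parametric, Mann-Whitney U tests will be used". That test is also unadjusted. The section closes with a plan to deal with confounding: "multivariable regression models will be generated to report the adjusted effect of which spine navigation technique is used on length of surgical time". It lists no covariates, and it does not say that this model decides non-inferiority.

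Section 4.1 (Sample Size Analysis) powers the study on the same two-sample t-test: 65 per group, alpha 0.05, margin 40 minutes, true difference 5 minutes, power 0.883. Its planning figures are: "Average length of surgery for 1, 2, and 3-level fusion surgeries are 230, 275, and 325 minutes, respectively" and "Estimated pooled standard deviation was set at 70 minutes, representing 22 to 30% of the mean operation time for the single and multi-level surgeries".

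On design, section 3.1 states: "This is a single center, non-randomized, prospective cohort study". The synopsis defines both arms by the same range of procedures. For the control arm it reads: "One, two and three-level posterior spine fusion surgery using bilateral pedicle screw instrumentation under 2D fluoroscopy". Number of levels otherwise appears only in the synopsis paragraph on exploratory work: "Exploratory analyses include the number of vertebral levels involved". I found no allocation rule, matching, stratification or quota by level.

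**The concern.** The protocol's own figures make number of levels a strong determinant of the primary endpoint, and the deciding test leaves it out. Two things follow.

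- **Bias.** If the arms differ systematically in level mix, the crude difference in means contains case mix as well as the effect of the navigation system. If MvIGS receives the easier cases, the study can declare non-inferiority falsely. If it receives the harder ones, the study can miss true non-inferiority. The documents do not show that the arms will differ, but nothing in the described design prevents it.
- **Lost power.** The t-test leaves between-level variation in its error term. That costs power even when the arms are perfectly balanced.

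**Working it through.** **Inputs.** From section 4.1: level means 230, 275 and 325; SD 70; margin 40; true difference 5; n = 65 per arm. *Assumed*, because the documents do not give it: the level mix. I use equal thirds, with 60/30/10 as a check.

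**1. The stated power.** The standard error is 70 × √(2/65) = 12.28. The noncentrality is (40 − 5)/12.28 = 2.85 on 128 df. One-sided alpha 0.05 gives power 0.883, which matches the protocol; one-sided 0.025 gives 0.808. The plan does not state sidedness, but its figure implies one-sided 0.05. Non-inferiority then needs an observed difference below 40 − 1.657 × 12.28 = 19.7 minutes.

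**2. Size of the level effect.** 275 − 230 = 45 and 325 − 275 = 50, so each step exceeds 40. These are contrasts between patients. The bias in the arm means is the sum over levels of (difference in arm shares × level mean).

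**3. No systematic shift: power.** The between-level variance is V = Σ p(mean − overall mean)².

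- Equal thirds: overall mean 276.7, V = 1505.6, between-level SD 38.8.
- 60/30/10: overall mean 253.0, V = 981, between-level SD 31.3.

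If 70 is within-level, the t-test works with √(4900 + V). If 70 is the total, the level-adjusted model works with √(4900 − V).

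| Reading of 70 | Mix | SD in t-test | SD in adjusted model | t-test power | Adjusted power |
|---|---|---|---|---|---|
| Within-level | Thirds | 80.0 | 70 | 0.798 | 0.883 |
| Within-level | 60/30/10 | 76.7 | 70 | 0.827 | 0.883 |
| Total | Thirds | 70 | 58.3 | 0.883 | 0.961 |
| Total | 60/30/10 | 70 | 62.6 | 0.883 | 0.936 |

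Section 4.1 does not say which reading applies. It relates 70 to the separate level means (70/325 = 21.5%, 70/230 = 30.4%), which suggests within-level.

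**4. Assumed systematic shift of 10 percentage points** (6 to 7 of 65 patients).

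- One- to two-level: 0.10 × 45 = 4.5 minutes.
- One- to three-level: 0.10 × 95 = 9.5 minutes.

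Power uses the effect 35 − bias (MvIGS has the harder mix, true difference 5). False non-inferiority uses the effect 0 + bias (MvIGS has the easier mix, true difference 40).

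| Bias | SD in t-test | t-test power | False non-inferiority |
|---|---|---|---|
| 4.5 | 70 | 0.796 | 0.100 |
| 4.5 | 76.7 | 0.729 | 0.095 |
| 4.5 | 80.0 | 0.697 | 0.092 |
| 9.5 | 70 | 0.663 | 0.191 |
| 9.5 | 76.7 | 0.595 | 0.173 |
| 9.5 | 80.0 | 0.565 | 0.166 |

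**5. Simulation** (20,000 runs, levels drawn at random within each arm).

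- With no shift, false non-inferiority is 0.048-0.053 for the t-test and 0.047-0.051 for the adjusted model. Chance imbalance is therefore not the problem.
- With the 10-point shifts, the adjusted model keeps false non-inferiority at 0.047-0.051. Its power is 0.873-0.876 if 70 is within-level and 0.928-0.959 if it is total.

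**The case against.** The strongest reply is that the plan already provides for adjustment. Section 4.2 commits to a multivariable regression on this same outcome, and the word used for its role is ordinary reporting language, not an explicit demotion. That is fair, and it is why this is not a fatal flaw. It does not close the gap: the covariates are open, and no rule says which result decides if the crude and adjusted analyses disagree.

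Four further points have weight.

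- **Patient contrast against margin.** The 45-50 minutes is a difference between patients, while the margin applies to arm means. A bias of 40 minutes would need the arms to differ by about 40/47.5 = 0.84 levels on average. The shifts examined here give only 4.5 and 9.5 minutes. Even so, the observed difference must fall below 19.7 minutes, so biases of that size matter.
- **Hypothetical shift.** The inflated error rates rest on an assumed shift. The adjusted model's recovery in simulation is by construction, because level is the only confounder simulated. Both points stand. The power argument needs no shift.
- **SD reading and mix.** Pooled may mean pooled over the two arms, and then the stated 88% is right for the t-test. Nor is 80-83% a bound: an 80/15/5 mix with 70 within-level gives about 85%. Adjustment gains power in every case computed, but the size of the gain is uncertain.
- **Other confounders.** Adjusting for level leaves the rest untouched, including the learning curve that section 1.2 describes for computer-assisted systems. That limits what the fix achieves. It is not a reason to omit the one factor that the protocol itself quantifies.

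**Conclusion.** The concern holds. The deciding test is unadjusted, the cohort is non-randomised and mixed by level, and the planned adjustment is neither specified nor linked to the margin.

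With no systematic shift, the type I error is sound and the cost is power: about 5 to 9 percentage points below the adjusted model if 70 is within-level (80-83% against 88%), or a gain of 5 to 8 points forgone if it is total (88% against 94-96%). On the within-level reading, the stated 88% is not the power of the planned t-test. Under an assumed 10-point shift, t-test power is 70-80% or 56-66%, and false non-inferiority is 9-10% or 17-19%, for biases of 4.5 and 9.5 minutes.

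The textual finding is firm. The magnitudes depend on the assumed level mix, the size and direction of any shift, and the reading of the SD. The change should be made, but the existing regression keeps this short of disqualifying.

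**What to change.** **Section 4.2**

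- Make the primary analysis a linear model of operative time on arm and number of fused levels (1, 2 or 3, as a categorical term).
- Declare non-inferiority if the upper one-sided 95% confidence bound of the adjusted difference (MvIGS minus fluoroscopy) is below 40 minutes. The one-sided 5% level is a choice that should be written down; it is the level that reproduces the stated 0.883.
- Keep the unadjusted t-test as supportive. Also keep the wider multivariable regression as supportive, with its covariates listed in advance.
- State that the Shapiro-Wilk/Mann-Whitney switch does not replace the primary model.

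**Section 4.1**

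- State whether 70 minutes is the within-level or the total SD, give the assumed level mix, and restate the power to match.

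**Cost.** A written amendment approved by the sponsor under section 7.1.1, two degrees of freedom, and no additional patients. Number of levels should already be available, since it is a listed exploratory item, although no data form is shown. The change protects against imbalance in level only.

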2.2 Secondary Endpoints

- Length of stay
 - Aim: Decrease length of hospital stay
 - Measured: Time (Hours)
- Length of time for initial image processing
 - Aim: Decrease disturbance to surgeon workflow
 - Measured: Time (Minutes)
- Length of time to place all screws
 - Aim: Reduce the time for screw placement
 - Measured: Time (Minutes)
- Length of time to confirm screw placement
 - Aim: Reduce the time needed for confirmation of screw location
 - Measured: Time (Minutes)
- Length of time to register images
 - Aim: To reduce time for registration of reference images
 - Measured: Time (Seconds)
- Estimated Blood Loss (EBL)
 - Aim: To reduce the EBL of each case
 - Measured: Milliliters (mL)
- Incidence of Malalignment
 - Aim: To decrease the incidence of pedicle screw malalignment
 - Measured: Misalignment angle between pilot hole and screw trajectory (degrees)
- Complications: Neurological Deficits, Dural Tears, deep wound infections, etc
 - Aim: To decrease the incidence of intraoperative complications
 - Measured: number of reported complications while hospitalized
- Measurement of 2D fluoroscopy radiation exposure
 - Aim: to reduce patient and surgeon exposure to radiation
 - Measured: Exposure measured by Dose Area Product (DAP)

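### Confounder adjustment is planned for surgical time only, so total time to place all screws, which rises with the number of levels, is compared unadjusted between two non-randomised arms

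*Combined protocol and SAP*

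**What the plan says.** Section 3.1 gives the design: "This is a single center, non-randomized, prospective cohort study to comparatively evaluate the implementation of the MvIGS spine navigation system". The Synopsis defines each arm by the same range of cases, "One, two and three-level posterior spine fusion surgery using bilateral pedicle screw instrumentation", under MvIGS guidance in one and 2D fluoroscopy in the other. No allocation rule, matching, stratification or cap by number of levels is stated.

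Section 2.2 lists "Length of time to place all screws" as a secondary endpoint, in minutes per patient, with the aim of reducing it.

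Section 4.2 assigns the tests:
- For continuous secondary outcomes the plan "will use independent samples t-tests to analyze length of hospital stay; time for initial image processing; time to place all pedicle screws", followed by confirmation time, registration time, blood loss and radiation.
- If normality fails: "For those that are non-parametric, Mann-Whitney U tests will be used".
- For binary outcomes, chi-square or Fisher's exact "tests will be used to compare differences in incidence of malalignment and rate of complications between the two study groups".
- For confounding: "multivariable regression models will be generated to report the adjusted effect of which spine navigation technique is used on length of surgical time". No covariates are named, and no other outcome is covered.

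Number of vertebral levels appears in the Synopsis as an exploratory analysis, with no method and no link to the secondary outcomes.

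**The concern.** The plan accepts that confounding is possible and then handles it for one outcome. Total screw-placement time is more directly exposed than most, because it is a sum over screws: a three-level case takes longer than a one-level case even if each screw goes in at the same speed. If one arm happens to contain more short constructs, its total falls and the planned test attributes the fall to the guidance technique. An imbalance in the other direction would hide a real gain. Mann-Whitney compares the same raw totals, so it gives no protection.

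Precision is also lost. The spread from 4 to 8 screws enters the error term of a two-sample test even when the arms are balanced. Screw placement is the step that navigation acts on most directly, so a misleading or imprecise result there matters to how the study is read.

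**Working it through.** **The plan's own figure.** Section 4.1 gives margin 40, true difference 5, SD 70, 65 per group and alpha 0.05. The effective distance is 40 − 5 = 35 minutes. A one-sided 0.05 t calculation on 128 df gives power 0.8831, which matches the stated 0.883. This point does not dispute the sample size.

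**Evidence in the plan that levels matter.** Section 4.1 gives mean operative times of 230, 275 and 325 minutes for one, two and three levels. Take a mix of 50/30/20% in one arm and 30/30/40% in the other:
- 0.5×230 + 0.3×275 + 0.2×325 = 262.5
- 0.3×230 + 0.3×275 + 0.4×325 = 281.5

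The arms differ by 19 minutes with no technique effect.

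**Assumptions for screw time (not in the documents).** Two screws per vertebra, so S = 4, 6 or 8. Time per screw X has mean 6 minutes and CV 30%, independent of S, so Var(X) = 1.8² = 3.24 and E(X²) = 36 + 3.24 = 39.24. The patient total is T = S·X, with Var(T) = E(S²)·E(X²) − [6·E(S)]². There are 65 patients per arm. The chance of a significant t-test is about Φ(difference/SE − 1.96); the opposite tail is negligible.

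**Larger imbalance, 50/30/20 v 30/30/40, same speed.**
- E(S) = 5.4 v 6.2, so the difference is 0.8 × 6 = 4.8 minutes.
- E(S²) = 31.6 v 41.2, so Var(T) = 190.2 v 232.8.
- SE = √[(190.2 + 232.8)/65] = 2.55, and the ratio is 1.88.
- Φ(1.88 − 1.96) ≈ 0.47. Simulation gives 47 to 48%.
- At CV 50%, E(X²) = 45, Var(T) = 372.2 v 470.2, SE = 3.60, ratio 1.33, and Φ(−0.63) ≈ 0.26 to 0.27.

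**Mild imbalance, 45/30/25 v 35/30/35, same speed.**
- E(S) = 5.6 v 6.0, so the difference is 2.4 minutes.
- E(S²) = 34.0 v 38.8, so Var(T) = 205.2 v 226.5.
- SE = 2.58, the ratio is 0.93, and Φ(0.93 − 1.96) ≈ 0.15. Simulation gives 15%.

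In both cases, simulated regression on arm and screw count, or a t-test on time per screw, rejects in about 5% of trials.

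**Equal mix (40/30/30 in both arms), true 15% faster placement.** E(S) = 5.8, E(S²) = 36.4, and the difference in totals is 0.15 × 34.8 = 5.22 minutes.
- Planned t-test: Var(T) = 217.3, and 0.7225 × 217.3 = 157.0 in the faster arm. SE = 2.40, ratio 2.18, power ≈ 0.58.
- Time per screw: difference 0.9, variances 3.24 and 2.34. SE = √(5.58/65) = 0.293, ratio 3.07, power ≈ 0.86 to 0.87.
- Regression on arm and screw count: simulated power is 83 to 84%.

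**The case against.** The strongest reply is that these are secondary outcomes, that the outcome which drives the sample size already has an adjusted model, and that the achieved level mix is unknown. All of that is true. It limits the priority of the point, but Section 4.2 still commits to between-arm tests on these outcomes, and the loss of precision needs no imbalance.

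The illustration is open to challenge. Minutes per screw, CV and level mixes are assumed, and the false-positive rate falls as CV rises. Total time is taken as exactly proportional to screw count, which favours the per-screw test; any fixed set-up time would weaken that advantage. Regression with screw count as a covariate allows for a fixed component, which is why it is the preferred form.

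Three stronger readings are tempting and are not supported:
- *Level mix alone could produce an apparent radiation reduction.* Sections 1.1 to 1.3 describe MvIGS as a system without intraoperative radiation. Any DAP difference would then be largely structural; level mix could alter its size but would hardly create it.
- *Nothing planned could reveal an imbalance.* The descriptive frequencies in Section 4.2 and the exploratory look at levels could. For the larger mix, chi-square = 2×6.5²/26 + 2×6.5²/19.5 = 7.58 on 2 df, p ≈ 0.02. For the mild mix it is 2×3.25²/26 + 2×3.25²/19.5 = 1.90, p ≈ 0.39, so an imbalance that triples the error rate could pass unremarked. Neither table adjusts anything.
- *Every secondary outcome needs regression.* Image-processing and registration times need not depend on screw count, a misalignment angle has no evident reason to grow with it, and sparse complications support only one or two covariates.

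**Conclusion.** The point holds for total time to place all screws. The plan would compare a patient total that rises with levels, without adjustment, between non-randomised arms. Under the stated assumptions and no true difference in speed, the planned test is significant in about 15% of trials with a mild imbalance and about 48% with a larger one (about 26% at CV 50%), against about 5% with screw count in the model. With equal mix and a true 15% gain, power is about 58% unadjusted, 83% adjusted and 86% per screw. These figures illustrate a mechanism and do not predict this study's result.

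Confirmation time and blood loss plausibly rise with levels, and length of stay possibly does, but the documents give no figures for them. The non-inferiority sample size is unaffected. The change should be made, but it does not threaten the primary comparison.

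**What to change.** In Section 4.2:
1. Analyse screw-placement time and confirmation time by linear regression on arm, with number of screws (or instrumented levels) as a named covariate. Give time per screw as an alternative analysis.
2. Extend the same level-adjusted regression to blood loss and length of stay.
3. State that the adjusted estimate, with its confidence interval, is the main between-arm result for these outcomes, and show the unadjusted comparison beside it.
4. Keep the planned tests for image-processing time, registration time and sparse complications. Do not use a log model for DAP if zeros occur.

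The covariate has to be written down, because the surgical-time model names none that could be carried over. The cost is a few sentences, a few extra models, and counting screws from the operative record. Sample size and patient procedures do not change.
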